- Cognitive dysfunction which limits the ability of the participant to adequately understand procedures and risks.
- Prisoners

- Pregnant Women

Special populations:

- Adults unable to consent: excluded from study
- Individuals -who are not yet adults: individuals who are less than 18 years old will be excluded from the study
- Pregnant women: Women who are known to be pregnant will not be recruited into the study. A pregnancy test will be administered to females prior to enrollment in TENS (or sham) treatment. Women who become pregnant before or during the 8-week TENS treatment period will be discontinued from the study. Women who become pregnant after the 8-week TENS treatment portion of the study will continue to be enrolled, and followed according to protocol guidelines (no information will be collected specifically on the pregnancy or fetus).
- Prisoners: excluded from study
- Neonates: not applicable

5) Number of Subjects*

This is a single-site study and 98 potential participants with newly-acquired spinal cord injuries will be enrolled. See section 22, for more information.

6) Study-Wide Recruitment Methods*

This is not a multi-center study. See section 21.

7) Study Timelines*

It is anticipated that subjects will be enrolled in the study for 12 months (see **Figure 5**, in section 10, below, for procedures timeline).

It is anticipated that enrollment of subjects will occur between November 1, 2016 and January 1, 2022. This enrollment end date is 12-months prior to the end of the funding cycle for this grant, which will allow for complete follow-up of all subjects before study termination.

The estimated date for the investigators to complete this study is October, 2022.

8) Study Endpoints*

The primary study endpoints/outcomes are: 1.) the percentage of subjects who develop chronic neuropathic pain at the 12-month post-spinal cord injury time point (as defined by a score of ≥ 2 on the Spinal Cord Injury Pain Inventory (SCIPI), a self-report scale of symptoms); and 2.) the severity of chronic neuropathic pain (as measured by a self-report rating of neuropathic pain symptoms) measured at the 12-month post-spinal cord injury time point. The secondary study endpoints/outcomes include other aspects of pain symptoms and physical and emotional function. All outcomes and other variables are listed in Table 2 and described in detail below, within the “Procedures Involved” section.

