Assessments of primary and secondary outcome measures will occur at the time points

diagramed in Figure 5. Details regarding the specific assessment tools and measures to be used are described below and listed in **Table 2**. The primary outcome variables for Aim 1 (Spinal Cord Injury Pain Instrument (SCIPI)⁸⁰ score of ≥ 2 , and Neuropathic Pain Symptom Inventory score⁸⁹) will be collected during each scheduled assessment (full and abbreviated assessments), with additional outcome measures recorded less frequently (during full assessment sessions only: 4 times during the study).

Randomization and blinding procedures:

A blocked randomization procedure will be used, so that for each eight patients enrolled, four will be allocated to TENS and four to Sham TENS. A computer-generated random assignment sequence will only be accessible to the study staff member responsible for delivering TENS treatments. The PI of the study, the researchers evaluating pain diagnoses, and the research subject will not be informed of the treatment allocation assigned. All subjects will be told that they may or may not feel the stimulation from the TENS unit during treatment sessions due to the parameters of the study. The stimulation parameters of the TENS unit will not be visible to the subject, so that subjects will not obviously know to which study group they were randomized.

Treatment procedures:

(a) *TENS device*: The TENS 7000 Dual Channel battery-powered digital stimulator (Roscoe Medical, Ohio, USA) will be used. This device provides for adjustable frequency/pulse rate, pulse width, and amplitude, as well as recording of session data (settings and duration of treatment session). The TENS 7000 device has two channels. Each channel will be connected to two self-stick square electrodes (thus, a total of 4 electrode pads will be used) with dimensions of 2 inches by 2 inches. New electrode pads will be used for each treatment session.

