- The Spinal Cord Injury Pain Instrument (SCIPI)⁸⁰ will be used to identify pains that are likely to be neuropathic in nature. This four-item questionnaire has shown sensitivity and specificity of 78% and 73%, respectively, for diagnosing neuropathic pain when using a cutoff score of ≥ 2 on this scale.⁸⁰ The pain classification definitions and guideline presented within the International SCI Pain Basic Data Set 2 (ISCIPIBDS2) will also be used to assist with classification of pain type.

This assessment will be used as the primary outcome measure for Aim 1, indicating the presence or absence of neuropathic pain at each follow-up time point.

ii. Pain intensity and symptoms:

Based on differentiated pains, as reported by the study subject, the intensity of each pain will be rated using a 0 – 10 numerical rating scale (NRS), with 0 being equal to “no pain” and 10 being equivalent to “pain as bad as you can imagine.” Subjects will be asked to “Rate your pain by indicating the number that best describes your pain on average over the past 24 hours,” “over the past week,” and “over the past 3 months.”

This scale, including the phrasing of the anchors and the recall time points, has been suggested as a primary

endpoint for chronic pain clinical trials.⁹² *Changes in pain intensity for neuropathic pains will be calculated across the assessment time points to measure the effectiveness of TENS treatment for those who present with neuropathic pain at baseline [Aim 1], and to assess correlations among pain severity and demographic and psychological factors [Aim 2].*

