Based on a total sample size of 98 subjects, and an estimated 15% drop-out rate, we expect that approximately 82 subjects will complete the study (i.e., 41 subjects per treatment arm). Based on previous work,^{21, 59} we project that 60% of subjects in the Sham TENS (control) group will have at- or below-level neuropathic pain at the 12 month follow-up time point. Thus, with 41 subjects in each group, $\alpha = 0.05$, power of at least 80%, and an analysis based on a two-sided Z-test (for group difference in proportion of subjects with neuropathic pain) for *Hypothesis 1a*, we will be able to detect at least a 50% reduction in the rate of subjects with chronic neuropathic pain in the TENS treatment group compared to the Sham group at 12 months post-SCI (i.e., Sham TENS = 60% with neuropathic pain; Treatment TENS = 30% neuropathic pain).

For t-test analyses assessing differences between groups (Sham vs. Treatment) using continuous variables (e.g., NRS, NPSI), 41 subjects in each group will allow for detection of a medium-to-large effect size (i.e., Cohen's $d = 0.6$) with α set at 0.05 and power of 0.80. Paired correlations will also be used for additional analyses (*Aim 2*). For correlations within group ($n = 41$), with power set at 0.80 and $\alpha = 0.05$, we will be able to detect a medium-to-large effect size (i.e., Cohen's $f^2 = 0.20$), and we will be able to detect a small-to-medium effect size for across-group analyses ($n = 82$; Cohen's $f^2 = 0.10$).

Data analysis plan:

Descriptive evaluations of the data will be performed for all variables to check the integrity of the data and to verify the underlying assumptions of the statistical tests that are planned. If necessary, and as appropriate, data will be transformed prior to any parametric analyses, or non-parametric techniques will be used with untransformed data. Statistical analyses will use two-tailed tests and an a-priori α of 0.05.

In addition to direct tests of hypotheses (described in detail below), descriptive analyses and graphical representations (e.g., spaghetti plots) of data will be used to describe longitudinal

characteristics of clinical pain, somatosensory function, and other physical and psychological outcomes across the 12-month timeline of study participation.

Hypothesis 1a:

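### Neuropathic pain severity is a primary outcome in sections 8 and 9 but secondary in section 11, and no rule says which outcome decides the trial

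*Combined protocol and SAP*

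**What the plan says.** All places are in the combined protocol and SAP.

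**Two primary outcomes.** Section 8 (Study Endpoints) gives the percentage of subjects with chronic neuropathic pain at 12 months, by a score of at least 2 "on the Spinal Cord Injury Pain Inventory (SCIPI), a self-report scale of symptoms", and then "2.) the severity of chronic neuropathic pain (as measured by a self-report rating of neuropathic pain symptoms", also at 12 months. The section 9 overview, before the randomisation heading, reads "The primary outcome variables for Aim 1 (Spinal Cord Injury Pain Instrument" with a cutoff of 2, "and Neuropathic Pain Symptom Inventory score". Section 12 says the interim looks compare the primary endpoints, in the plural. It lets either reduced development of neuropathic pain or a substantial reduction in its severity lead to a change in protocol.

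**One primary outcome.** Section 9, Pain classification, says of the SCIPI-based classification: "This assessment will be used as the primary outcome measure for Aim 1". Section 11, Power / sample size, bases Hypothesis 1a on a two-sided z test "for group difference in proportion of subjects with neuropathic pain". Section 11, Hypothesis 1a, makes the two-proportion z test on SCIPI-based presence the primary analysis and puts NRS and NPSI severity among the secondary outcomes. It adds that the severity comparison matters especially if the primary analysis shows no difference in rates.

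**Alpha.** Section 11 sets one level for everything: "Statistical analyses will use two-tailed tests and an a-priori" alpha of 0.05. No split, testing order or success rule is given.

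**Presence.** Section 8 uses the SCIPI cutoff alone. Section 11 also requires the pain to be at or below the level of injury and, for subjects with symptoms before entry, a rating of at least 4 out of 10.

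**The concern.** The same outcome is primary in one part of the document and secondary in another, and nothing says which part takes precedence. If section 11 governs, one test decides the trial. Under section 8 and the section 9 overview, a null SCIPI result with a significant severity result could be presented as a met primary endpoint. The document does not state that reading, but it does not exclude it either. The section 11 remark on severity after a null primary, and the either/or trigger in section 12, both lean towards it. With about 82 completers such a split result is plausible. Two readers could then reach opposite conclusions, each citing the protocol, and a choice made after unblinding would not be credible.

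**Working it through.** **1. The plan's own figure.** Inputs from section 11: 41 completers per arm, 60% vs 30%, two-sided 0.05, power of at least 80%.
- Pooled formula: z = (0.3·√41 − 1.960·√(2·0.45·0.55)) / √(0.6·0.4 + 0.3·0.7) = (1.921 − 1.379)/0.671 = 0.808, so power is 79.0%.
- Unpooled: 0.3/√(0.45/41) − 1.960 = 2.864 − 1.960 = 0.904, so power is 81.7%.

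The stated 80% is reproduced. It is power for the SCIPI proportion at the full 0.05, so the sample size for Hypothesis 1a already treats that test as the deciding one.

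**2. Error if either outcome may succeed.** Two two-sided tests at 0.05, both null hypotheses true:
- Independent tests: 1 − 0.95² = 0.0975.
- In favour of TENS only: 1 − 0.975² = 0.0494, against 0.025 for one test.

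The two outcomes will be positively correlated, but the documents give no correlation. Assumed values, with a bivariate normal for the two test statistics:

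| Correlation (assumed) | At least one significant | False benefit |
|---|---|---|
| 0 (upper bound) | 9.75% | 4.9% |
| 0.5 | 9.1% | 4.5% |
| 0.7 | 8.4% | 4.2% |
| 0.9 | 7.0% | 3.5% |

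**3. How far the correlation can be narrowed.** Suppose every SCIPI-negative subject scores zero on severity. With prevalence p = 0.6 and coefficient of variation CV of severity among positives, the correlation is √((1 − p)/(CV² + 1 − p)). That gives √(0.4/0.49) = 0.90 at CV 0.3 and √(0.4/1.4) = 0.53 at CV 1.0, hence 7.0% to 9.0%.

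The zero-score assumption is doubtful. Section 9 gives the SCIPI a sensitivity of 78% and a specificity of 73%. Suppose instead that 60% truly have neuropathic pain and only they score above zero:
- P(SCIPI positive) = 0.6·0.78 + 0.4·0.27 = 0.576.
- Covariance with severity, in units of mean severity among those with pain: 0.468 − 0.576·0.6 = 0.1224.
- Correlation = 0.1224 / (√(0.576·0.424)·√(0.6·CV² + 0.24)) = 0.46 at CV 0.3 and 0.27 at CV 1.0.
- Familywise error: about 9.2% and 9.6%.

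The 4/10 rule also leaves some subjects negative with non-zero severity, which again lowers the correlation. The bound of 9.75% is therefore the firm figure; the values beneath it are illustrations.

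**4. Other ways to remove the conflict, at 41 per arm.**
- Equal split, 0.025 each: the z test falls from 79.0% to 69.6% power (pooled formula). Restoring 80% needs 51 per arm, that is 102 completers and 102/0.85 = 120 enrolled, against 98.
- Both must succeed: joint power cannot exceed that of the weaker test. At the plan's d = 0.6 the t test has 76.5% power, so 76.5% is a ceiling.

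**The case against.** The best defence is that section 11 is the only analysis plan in the document. It names one primary analysis, and Hypothesis 1a is sized on it. Section 9 is itself split, since its SCIPI description names that measure alone, and its NPSI sentence does not tie the NPSI to 12 months. The plural in section 12 concerns monitoring and sets no final success rule. All of this stands and favours SCIPI as the deciding outcome. But section 11 neither claims precedence over section 8 nor states a success rule.

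Three stronger readings are tempting, and the documents do not support them.
- A reader might infer that the plan adopts an either-outcome rule, so that its type I error is 9.75%. No passage says so. Hypothesis 1a speaks of prevalence and severity together, which could equally mean that both must succeed.
- A reader might infer that the severity instrument in section 8 is free to be chosen later between NPSI and NRS, because section 9 says of the NRS: "This scale, including the phrasing of the anchors and the recall time points, has been suggested as a primary" endpoint for chronic pain trials. That remark is general. Section 8 refers to section 9 for detail, and section 9 names the NPSI score as primary and describes its total as the measure of neuropathic pain severity. That largely settles NPSI.
- A reader might count NRS and NPSI as two further primaries, giving 1 − 0.95³ = 14.3%. Only section 11 lists both for the 12-month comparison, and there they are secondary.

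**Conclusion.** The point holds as an unresolved contradiction about which outcome decides the trial, and it must be fixed before the final unblinded analysis. The error figures are conditional. If either outcome may succeed at two-sided 0.05, familywise error is above 5% and at most 9.75%, and false benefit is at most 4.9% against 2.5%. Anything narrower depends on an assumed correlation. If section 11 governs, or if both outcomes must succeed, there is no inflation. The differing definitions of presence are a related inconsistency to settle in the same amendment. They concern how the SCIPI endpoint is defined, not which endpoint decides. Error from the looks after each 20 completers is a separate issue and is not in these figures.

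**What to change.** Amend sections 8, 9 and 12 to follow section 11.
- **Single primary:** SCIPI-based presence at 12 months, two-sided 0.05. Use one definition in sections 8 and 11, stating explicitly the location requirement and the 4/10 threshold that section 11 adds.
- **Key secondary:** NPSI total score at 12 months, compared between randomised groups in all subjects as section 11 implies. Test it at 0.05 only if the primary is significant, and state how subjects without neuropathic pain are scored.
- **Supportive:** the NRS, and severity change in subjects symptomatic at entry. The section 9 overview and the NPSI description there both describe that subgroup use, so reconcile those passages explicitly with the all-subject comparison.
- **Null primary:** say that severity results are then exploratory.
- **Section 12:** make its reference to primary endpoints consistent with the above. No change to its decision criteria is proposed here.

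Date the amendment before the final unblinded analysis, and record its reason and which interim between-group results had been seen.

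The cost is a document change with no new data or subjects, and the full 0.05 stays with the test the trial was sized on. There are two downsides. Severity cannot be claimed as confirmatory after a null primary. A declared primary is also demoted late: this version is dated 7-18-2022, after the planned January 2022 end of enrolment and about three months before the estimated October 2022 completion.

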Modality	SCI		Nondisabled	
	ICC (95% CI)	# total test sites	ICC (95% CI)	# total test sites
Log MDT	0.84 (0.75-0.90)	56	0.63 (0.45-0.76)	58
Log VDT	0.90 (0.84-0.94)	67	0.86 (0.79-0.91)	80
Log CDT	0.90 (0.83-0.94)	55	0.68 (0.54-0.78)	80
Log WDT	0.95 (0.91-0.97)	50	0.70 (0.57-0.80)	79
CPT	0.50 (0.28-0.67)	56	0.49 (0.31-0.64)	80
HPT	0.50 (0.28-0.66)	62	0.68 (0.55-0.79)	79

MDT = mechanical detection threshold; VDT = vibration detection threshold; CDT = cool detection threshold; WDT = warm detection threshold; CPT = cold pain threshold; HPT = hot pain threshold

severity of chronic neuropathic pain symptoms, in participants with chronic SCI.^{6, 8, 74} **Figure 4** shows that, in test sites in body areas where neuropathic pain symptoms were present, lower pain thresholds (i.e., increased pain sensitivity) were associated with more severe neuropathic pain scores.

Thus, previous work by the study investigators demonstrates that the study is feasible and that they have the skills and tools necessary to perform the proposed study. Results from this body of work support the rationale of the proposed site-specific study.

Figure 4: Pain threshold is negatively related to severity of NeuP in those with SCI

Subjects with SCI and NeuP ($n = 22$) completed sensory testing at sites within the area affected by NeuP. Thresholds were also obtained in control subjects at the same test sites on the body and used to calculate z-scores for the thresholds obtained in those with SCI. Subjects with less loss of pain sensation (z-scores close to 0) had significantly higher NPSI scores than those with greater loss of pain sensation (higher z-scores).⁷⁴ (Z-scores reflect the degree to which thresholds in participants with SCI vary from the distribution of thresholds obtained in nondisabled control subjects, and allow for comparison of measures obtained at different locations on the body.)

4) Inclusion and Exclusion Criteria*

Inclusion criteria:

- Age ≥ 18 ;
- Traumatic spinal cord injury;
- Date of injury occurring within four months of study enrollment.

Exclusion criteria:

- More than four months since date of injury;
- Contraindications for the study intervention, transcutaneous electrical nerve stimulation (TENS),⁸⁸ including:
 - Implanted electronic device such as a pacemaker;
 - Cardiovascular problems;
 - Pregnancy;
 - Epilepsy;
 - Cancer;
- Persons with a spinal cord injury at the C2 level, as placement of TENS electrodes on the neck is not recommended;

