Safety endpoints include frequency and severity of adverse events and increased likelihood of developing chronic pain due to TENS treatment. Please see section 13: “Provisions to monitor the data to ensure the safety of subjects,” describes the monitoring of the safety endpoints.

[figure not shown]
9) Procedures Involved*

Overview:

The primary study design will be a randomized, double-blinded, controlled trial of early intervention TENS compared to Sham TENS, with longitudinal tracking of signs and symptoms of NeuP, as well as symptoms and severity of non-neuropathic pains, pain impact, and psychological function, for 12 months post-SCI. **Figure 5** diagrams the study procedures, subject flow, and assessment time points.

Patients will be eligible for recruitment into the study as soon as they have been admitted to the SCI inpatient rehabilitation unit at UM/JMH/Lynn Rehabilitation Center (see Section 21 for full recruitment procedures). Treatment TENS or Sham TENS sessions (see “Randomization procedures,” below) will be initiated within four months post-injury (with four weeks post-injury as the target, if feasible).

Figure 5: Timeline of subject participation and study procedures

* Note the above diagram depicts the anticipated average time course of study procedures across subjects. Due to varying times between injury and admission to/discharge from inpatient SCI rehabilitation, not all subjects will begin participation in the study precisely at the two-month post-injury timepoint.

Subjects will be enrolled and randomized regardless of whether they have NeuP symptoms at initial assessment. Because approximately 25% of SCI patients who report chronic neuropathic pain at 1 year post-injury had initial neuropathic pain symptoms at 1 month post- injury,²¹ initiating treatment at four weeks post-injury will capture approximately 75% of patients before their neuropathic pain symptoms manifest. In those patients who do have neuropathic pain symptoms at the baseline assessment, we will be able to test the ability of TENS to interfere with the transition from acute to chronic neuropathic pain, by comparing the decrease in severity of neuropathic pain symptoms from baseline to 12 months post-injury between the two study groups (Treatment TENS vs Sham TENS).

Once baseline assessments are completed, treatment will be administered twice a week, for 30 minutes each session, for 8 weeks.

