The primary statistical analysis, to test the effectiveness of prophylactic TENS for neuropathic pain after SCI will be via a two-proportion z test, comparing the percentage of subjects in the TENS treatment group who are “positive” for neuropathic pain at 12 months post-injury to the percentage of subjects in the Sham TENS group who are positive for neuropathic pain at 12 months post-injury. Subjects who score a 2 or more on the SCIPPI for a pain located at or below their neurological level of injury at the 12 month follow-up time point will be considered positive for neuropathic pain. Subjects who do not have a pain at- or-below the level of injury or a score of 2 or more on the SCIPPI will be considered negative for neuropathic pain. For those subjects who have neuropathic pain symptoms early after injury (i.e., prior to entering the study), a “positive” result for neuropathic pain will be defined as having neuropathic pain that is moderate or greater (rated at least a 4 out of 10) at the 12 month follow-up assessment.

Additional analyses will be conducted using secondary outcomes collected at the 12-month time point: 1) comparison of pain severity (using the NRS and NPSI scores) between the groups (This analysis will be especially important if the primary analysis does not show a difference in rates of the presence of neuropathic pain at 12 months.); 2) comparison of use of analgesics between groups; and 3) comparison of response to pain interference questions from the ISCPBDS2. General linear model analyses will be used, with TENS group (Treatment vs. Sham) as a categorical predictor of these secondary outcome measures.

Separate analyses for at-level neuropathic pain and below-level neuropathic pain, as well as nociceptive pains, will also be conducted to examine whether TENS differentially impacts their development or severity. Additional analyses will be conducted, using the diagnosis of each pain type according to ISCPBDS guidelines, as determined and agreed upon by our study staff pain experts, as a confirmation of the primary neuropathic pain metric (SCIPPI ≥ 2).

Hypothesis 1b:

To investigate factors that may be related to patient responsiveness to TENS as a preventive treatment for chronic neuropathic pain, we will assess correlations between changes in evoked pain (before and after TENS treatments) and the presence and severity of neuropathic pain

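### The 75% pre-onset figure is unsupported for starts after four weeks, and the pooled primary test cannot by itself show an effect on new onset

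*Combined protocol and SAP*

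**What the plan says.** Section 9 (Procedures Involved, Overview) takes from a cited cohort that about 25% of patients with chronic neuropathic pain at one year already had symptoms at one month. It concludes that "initiating treatment at four weeks post-injury will capture approximately 75% of patients before their neuropathic pain symptoms manifest". The same section makes four weeks a target, to be met where feasible, and lets treatment start up to four months after injury. Section 4 sets the entry window as "Date of injury occurring within four months of study enrollment". The note to Figure 5, which describes the expected average time course, says that "not all subjects will begin participation in the study precisely at the two-month post-injury timepoint".

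Subjects are randomised whether or not they have neuropathic pain at the first assessment. Allocation is in blocks of eight, and no stratification is described. Section 8 words the first primary endpoint as "the percentage of subjects who develop chronic neuropathic pain at the 12-month post-spinal cord injury time point". Section 11 (Hypothesis 1a) says that the primary analysis "to test the effectiveness of prophylactic TENS for neuropathic pain after SCI will be via a two-proportion z test". All subjects enter that one test. Those without earlier pain are positive on a SCIPI score of 2 or more for a pain at or below the injury level. Those with symptoms before entry are positive if neuropathic pain is rated at least 4 out of 10 at 12 months. For subjects with baseline pain, section 9 plans a between-arm comparison of change in severity. No comparison is planned in subjects free of neuropathic pain at entry.

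**The concern.** Aim 1 asks whether early TENS lowers the risk of developing chronic neuropathic pain and whether it reduces severity. Pain that has not yet begun and pain already present at first treatment are different targets, and an intervention may affect one and not the other. The share already in pain matters for reading the primary result. The only figure offered for it is conditional on a start that the protocol does not require and does not expect on average.

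The pooled rate could fall because existing pain dropped below 4 out of 10, and the result could then be reported as prevention. Conversely, a real effect on onset could be diluted by subjects already in pain and reported as absent. The wording of sections 8 and 11 (develop, prophylactic) invites both readings.

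**Working it through.** **1. The plan's own power.** Section 11 assumes "with 41 subjects in each group, $\alpha = 0.05$, power of at least 80%, and an analysis based on a two-sided Z-test", with "Sham TENS = 60% with neuropathic pain; Treatment TENS = 30% neuropathic pain". The normal approximation, with the null variance pooled, gives

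Φ[(0.30 − 1.96·√(2·0.45·0.55/41)) / √((0.60·0.40 + 0.30·0.70)/41)] = Φ[(0.300 − 0.215)/0.105] = 79%.

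The unpooled version gives 82%, and exact binomial enumeration of the pooled z-test gives 81%. For drop-out, 98 × 0.85 = 83.3, close to the stated 82 completers. The plan's figures reproduce.

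**2. What the 75% is a share of.** It is 1 − 0.25, so its denominator is eventual cases. With 60% prevalence, eventual cases already in pain at one month are 0.25 × 0.60 = 15% of all patients. If no early pain resolves, 85% of all patients are pain-free at one month; if some resolves, fewer are. The documents give no onset figure for any later month.

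**3. Illustration for later starts.** These assumptions are not in the documents:
- onset among eventual cases rises linearly from 25% at month 1 to 100% at month 12;
- 80% of subjects in pain at entry are positive at 12 months under sham;
- all subjects start in the same month.

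The 60% sham rate and 41 per arm are the plan's. For a start at month m:
- share of eventual cases already in pain: f = 0.25 + 0.75(m − 1)/11
- share of all subjects in pain at entry: b = 0.60f/0.80
- sham rate in the pain-free: q = (0.60 − 0.80b)/(1 − b)
- TENS rate if it only halves onset: 0.80b + (1 − b)q/2
- TENS rate if it only resolves existing pain (80% to 20%): 0.20b + (1 − b)q

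Month 2 as an example: f = 0.318; b = 0.191/0.80 = 0.239; q = 0.409/0.761 = 0.537. Onset only: 0.191 + 0.761 × 0.269 = 0.395. Resolution only: 0.048 + 0.409 = 0.457.

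| Start | f | b | q | Onset halved only | Power | Existing pain resolved only | Chance of p < 0.05 |
|---|---|---|---|---|---|---|---|
| Month 1 | 25% | 19% | 55% | 60% v 38% | 57% | 60% v 49% | 19% |
| Month 2 | 32% | 24% | 54% | 60% v 40% | 49% | 60% v 46% | 28% |
| Month 4 | 45% | 34% | 50% | 60% v 44% | 35% | 60% v 40% | 49% |

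Power is by exact enumeration. The normal approximation runs about 2 to 4 points lower. If TENS only halves existing pain (80% to 40%), significance occurs in 12%, 16% and 26% of trials.

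**4. Power in subjects pain-free at entry.** Suppose no early pain resolves and f = 25%. Then 41 × 0.85 ≈ 35 per arm are pain-free, with a sham rate of 0.45/0.85 = 52.9%. Halving it to 26.5% gives 62% power, and the 95% CI half-width is 1.96·√((0.529·0.471 + 0.265·0.735)/34.85) ≈ 22 points. At an assumed f = 50%, about 29 per arm are pain-free (42.9% v 21.4%) and power is 41%. Under the assumptions of step 3, power is 64%, 58% and 47% for starts at months 1, 2 and 4.

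**The case against.** The best defence is that Hypothesis 1a concerns the prevalence and severity of chronic neuropathic pain at 12 months. A randomised comparison of 12-month prevalence answers that without bias, whatever the mix at entry. This stands. A reader might infer that the pooled test is invalid or answers no question of interest; the documents do not support that.

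A reader might also infer that someone with pain at entry cannot develop the endpoint. Section 3 defines chronic as lasting three months or more, so a subject with recent pain may not yet have the chronic condition. Section 9 says openly that TENS is being tested against the transition from acute to chronic pain. The line between prevention and reversal is therefore less sharp than the terms suggest.

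The plan does treat subjects with earlier pain separately, through the 4-out-of-10 rule. But that rule feeds the same pooled test, so it makes the mixture explicit without separating it.

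Nor is the 75% shown to be wrong. Section 3 says onset often comes at least a few months after injury, and later text expects most subjects to be pain-free at enrolment. No later figure is given, so the linear curve and 80% persistence are illustrative only.

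A significant result from resolution alone is possible but not the likely outcome in any row of the table, and the 80% to 20% effect there is larger than the relative halving the plan assumes. Chance imbalance in baseline pain is already allowed for in the test's error rate. Finally, a stratified test alone still returns one verdict; only the stratum estimates speak to onset.

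**Conclusion.** The point holds as one of attribution, not bias. For the start times this trial permits and expects, the 75% is unsupported, and even at four weeks it describes eventual cases, not all patients. The planned primary result supports a statement about 12-month prevalence but not, by itself, one about new onset. The data to go further are collected, but no such analysis is planned.

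Under the stated assumptions, a pure halving of onset would be detected in about 35-57% of trials, against about 80% for the planned effect. A pure effect on existing pain would be significant in about 19-49%. These ranges cover starts at months 1 to 4 and move with the onset curve, the persistence figure and the assumed effects.

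**What to change.** - Analyse the Hypothesis 1a binary endpoint stratified by neuropathic pain status at baseline (for example by Mantel-Haenszel), and state which baseline measure assigns status. The SCIPI and ISCIPBDS2 are already collected then, and the section 11 positive rule already needs this status.
- Pre-specify the risk difference with 95% CI in each stratum.
- Rest any claim about preventing onset on the estimate in subjects pain-free at entry, and describe the pooled result as an effect on 12-month prevalence.
- Replace the 75% in section 9 with the share actually pain-free at first treatment.
- Reconcile the wording of sections 8, 9 and 11.

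This version is dated 18 July 2022, after the planned end of enrolment, and section 12 plans comparisons of the arms after every 20 completers. The change should therefore be documented and dated before the final unblinded comparison.

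The cost is small: no new data and no change to entry, treatment or allocation. In simulation with the rate halved in both strata, the stratified test had 79-81% power against 81-82% for the z-test, with size of 5%. The real limitation is precision. The pain-free comparison has only about 62-64% power for a halving even in the most favourable cases worked above, and less with later starts, so it should be reported as an estimate with its interval and not as a powered test.
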